1. INTRODUCTION

[REDACTED]

[REDACTED]

[REDACTED]

1.1. Summary of Change

Major revisions from the 19 September 2013 version to the current version are:

- The efficacy evaluable population has been substituted for the per-protocol population for the analysis of the following endpoints: overall response rate (ORR), time to response (TTR), duration of response (DoR), time to progression (TTP), progression free survival (PFS) and overall survival (OS).
- Removal of all sub-group analyses.

The following aspects of data handling methods are modified with more details added:

- Additional censoring and event rules for PFS and DoR.
- Correction of the calculation for cycle length.
- Clarification of the definition of 'baseline'.

The following points are additions to this SAP version:

- Clarification that the PK and PD related table, figures and listings will be provided in a separate delivery document.
- Clarification that the cytogenetic sub-group analysis will be provided in a separate report.
- Identification of drug classification groups of prior anti-multiple myeloma (MM) drugs.
- Additional imputation rules for incomplete dates with regards to diagnosis date, prior and subsequent anti-myeloma therapy dates.

2. OBJECTIVES

The primary objective of the study is to evaluate the safety of the combination of POM and LD-DEX in a large cohort of subjects with refractory MM or relapsed and refractory MM.

The secondary objectives of the study are to:

- Analyze the population pharmacokinetics of POM and assess POM exposure response relationships in subjects with refractory MM or relapsed and refractory MM administered POM and LD-DEX.
- Evaluate efficacy of the combination of POM and LD-DEX in subjects with refractory MM or relapsed and refractory MM.
- Evaluate the relationship between cytogenetic profiles and the combination of POM and LD-DEX in terms of response and outcome.

[REDACTED]

3. INVESTIGATIONAL PLAN

3.1. Overall Study Design and Plan

This study is a multicenter, single-arm, open label study of POM in combination with LD-DEX in subjects with refractory or relapsed and refractory MM. Approximately 720 subjects who satisfy study inclusion and exclusion criteria will be enrolled into the study (for detailed subject eligibility see sections 7.2 and 7.3 of Protocol CC-4047-MM-010). There are three periods to this study: The screening period (defined as days -28 to 0 prior to start of the investigational product [IP]), the Treatment period starting at the moment of first administration of the IP defined as Cycle 1 Day 1 until start of follow-up, and the Follow-up period which starts at the time of the permanent IP discontinuation and which continues until all subjects have been followed for up to 5 years after the last issued interactive voice/web response system (IVRS/IWRS) enrollment date if still alive and not lost-to-follow-up, or longer if clinically relevant.

Subjects will undergo screening within 28 days prior to Cycle 1 Day 1 and be treated in 28-day cycles. Subjects will remain on treatment with the IP until a specific event, including, but not limited to, progressive disease (PD), intolerance due to toxicity, death, withdrawal of consent, non-compliance with the IP, and becoming lost-to-follow-up.

An outline of study time points and corresponding assessments due at those times are presented in Table 1: Table of Events (see section 5 of Protocol CC-4047-MM-010). Safety assessments will be performed during the Screening period and on Day1 (± 1 day) of each cycle as well as the time of IP discontinuation. Additional safety assessments (hematology, serum chemistry and estimation of renal function) shall be performed on day 15 (± 2 days) of cycles 1 to 6 while vital signs shall also be collected at a follow-up visit to take place within 28 days post discontinuation of the IP.

Pregnancy testing for females of child bearing potential (FCBP) and pregnancy counseling shall be assessed during the Screening period, Day 1 (± 1 day) of each cycle and at the time of the IP discontinuation. An additional pregnancy test for FCBP shall be conducted within 28 days post IP discontinuation.

Efficacy measurements shall be collected during the Screening period, at Day 1 (± 1 day) of each cycle and within 28 days post IP discontinuation, with the exception of response assessments which will not be collected during the Screening period. Survival status and recording of subsequent anti-myeloma regimens will be recorded within 28 days post IP discontinuation and during the Follow-up period every 3 months (84 ± 14 days).

Note that the visit (or assessment) occurring just prior to initiation of the IP is defined as “baseline” (i.e., Day 1 of Cycle 1). However, data from the Screening period will be substituted for a given measure if data at Day 1 Cycle 1 is not available.

Dose modifications and interruptions of the IP are permitted throughout the study.

Subjects will remain on study until a specific event, including, but not limited to, becoming lost-to-follow-up, death and withdrawal of consent.

The first full analysis of the primary and secondary endpoint will be conducted once all enrolled subjects have completed up to 2 cycles of the IP if having not stopped therapy earlier.

A final, updated, analysis will be conducted at the time of study close, the point when all subjects will have discontinued from the study, i.e. 5 years from the last issued IVRS enrollment date if having not discontinued from the study before this point.

3.2. Study Populations

The study population includes refractory MM subjects or relapsed and refractory MM subjects. All subjects must have documented progressive disease (PD) on or within 60 days of their last treatment, after receiving at least 2 lines of treatment, and must have received a minimum of 2 consecutive cycles of prior treatment regimens that included bortezomib and lenalidomide, either in combination or in separate regimens. These include:

- Subjects classified as *refractory* must have progressed during or within 60 days of treatment with bortezomib and/or lenalidomide.
- Subjects classified as *relapsed*, who previously responded to bortezomib and/or lenalidomide with at least partial response (PR) must have progressed within 6 months of ending treatment with bortezomib and/or lenalidomide.
- Subjects who have not achieved at least minimal response (MR) who have developed *intolerance or toxicity* after a minimum of 2 cycles of bortezomib.
- Subjects who are eligible for or who are planning to receive bone marrow transplant are not eligible for this study.

3.3. Study Endpoints

The primary endpoint is:

- The incidence of adverse events (AE) (type, frequency, seriousness, severity, relationship to POM and /or DEX, and outcomes), including second primary malignancy (SPM).

The secondary endpoints are:

- POM exposure
- POM population PK and exposure response
- Overall response rate (ORR)

- Time to response (TTR)
- Duration of response (DoR)
- Progression free survival (PFS)
- Time to progression (TTP)
- Overall survival (OS)
- Analysis of cytogenetic profiles

3.4. Stratification , Randomization and Blinding

Subjects will not be randomized or blinded due to the study being a single-arm study.

3.5. Sample Size

Approximately 720 subjects across twenty-one European countries will be enrolled into this study. This sample size has been determined to enable the characterisation of currently infrequent AEs. As such, a sample size of 720 subjects will allow detection of any infrequent AE, defined as an AE with a frequency of 0.4% (3/720), assuming a study power of 95%. Under this calculation, an infrequent event with a frequency of 0.4% will be confirmed if at least 1 of 720 evaluable subjects experiences such an event.

4. GENERAL STATISTICAL CONSIDERATIONS

In general and unless otherwise noted, continuous variables will be summarised using the following summary statistics; N, Mean, Standard Deviation, Median, Minimum and Maximum. Categorical variables will be summarized using frequency tabulations (i.e., counts and percentages). In the case of missing categorical data, an “unknown” category will be created for reporting purposes, but subjects or records included in this category will not be included in the denominator when calculating percentages.

4.1. Reporting Conventions

Summary tables, listings, and any supportive SAS output will include a “footer” of explanatory notes that will indicate, at a minimum, the following:

- Program source (e.g., SAS program name and the path that generates the output)
- Data extraction date (e.g., the database lock date, run date)

The purpose of the data extraction date is to link the output to a final database, either active or archived, that is write-protected for replication and future reference. An output date will also appear on each output page and will indicate the date the output was generated by the analysis program. Individual source listings will display all the relative values supporting corresponding tables and figures.

4.1.1. Dates Handling

Dates will be stored as numeric variables in the SAS analysis files and reported in DDMMMYYYY format (i.e., the [Date9](#). datetime format in SAS). Dates in the clinical database are classified into the categories of procedure dates, log dates, milestone dates, outcome dates, and special dates.

- **Procedure Dates** are the dates on which given protocol-specified procedure are performed. They include the dates of laboratory testing, physical examinations, tumor scans, etc. They should be present whenever data for a protocol-specified procedure is present and should only be missing when a procedure is marked as NOT DONE in the database. Procedure dates will not be imputed.
- **Log Dates** are dates recorded in the case report form (CRF) data logs. Specifically, they are the start and end dates for AEs and concomitant medications/procedures. They should not be missing unless an event or medication is marked as *ongoing* in the database. Otherwise, incomplete log dates will be imputed according to the rules in Appendix A of this SAP: Date Imputation Guideline (e.g., for duration or cycle assignment etc.). However, in listings, log dates will be shown as recorded without imputation.

- **Milestone Dates** are dates of protocol milestones such as enrollment date, study drug start date, study termination, etc. They should not be missing if the milestone occurs for a subject. They will not be imputed.
- **Outcome Dates** are dates corresponding to study endpoints such as survival, disease progression, etc. In most cases they are derived either from a milestone (e.g., the survival date is derived from the death date), or a procedure date (e.g., the progression date is derived from the date of the tumor scan that was used to determine progression). They may be subject to endpoint-specific censoring rules if the outcome event, for instance, did not occur; otherwise they are not subject to imputation.
- **Special Dates** cannot be classified in any of the above categories and they include, for example, the date of birth. They may be subject to variable-specific censoring and imputation rules (see Section 4.1.2. below).

Dates recorded in comment fields will not be imputed or reported in any specific format.

4.1.2. Calculation Using dates

Calculations using dates (e.g., subject's age or relative day after the first dose of the IP) will adhere to the following conventions:

- Study days after the start day of study drug will be calculated as the difference between the date of interest and the first date of dosing of the IP plus 1 day. The generalised calculation algorithm for a relevant day is:

$STUDY\ DAY = [(TARGET\ DATE - DSTART) + 1]$, where DSTART = the start day of study drug.

Study days before the start day of study drug will be calculated as the difference between the date of interest and the first date of the IP.

Note that Study Day 1 is the first day of treatment of study drug. Negative and zero study days are reflective of observations obtained during the baseline/screening period. Note: Partial date for the first study drug is not imputed in general. All effort should be tried to avoid incomplete study drug start date.

- For all efficacy analyses, time-to-event days for efficacy endpoints will be calculated as the difference between the date of event and the enrollment date plus 1 day.
- Age (expressed in days) is calculated as:

$AGE = [CONSENT - DATE\ OF\ BIRTH + 1]$, where CONSENT = the date the informed consent document (ICD) was signed.

In practice, age will be transformed into years by dividing the difference by 365.25 days, then truncating the divided difference to the nearest year.

- Prefer using calculated age from clinical database. When not available, may use calculated age from the CRF or the IVRS

- Partial birth date: impute a missing day as the 15th day of the month; impute a missing month as July; set age as missing if year is missing
- Intervals that are presented in weeks will be transformed from days (as calculated above) to weeks by using (without truncation) the following conversion formula:
$$\text{WEEKS} = \text{DAYS} / 7$$
- Intervals that are presented in months will be transformed from days (as calculated above) to months by using (without truncation) the following conversion formula:
$$\text{MONTHS} = \text{DAYS} / 30.4167$$

4.1.3. Calculation of Cycles

The start date of each treatment cycle will be calculated based on study drug exposure records for each subject. The start date of the first cycle will be the date when the subject receives any study drug.

Once the start dates, e.g., S_1, S_2, S_3, \dots are calculated, the end date of each cycle is calculated as the day before the start date of the following cycle, i.e., $E_i = S_{i+1} - 1$. For the last cycle, the end date (if missing or less than 28 days after start of cycle) will be calculated as the start date plus the prescribed cycle length (28) - 1, or the death date, or the discontinuation date, whichever is earlier.

The cycle number for each date of interest, e.g., AE or lab, will be calculated based on the cycle window set by their start and end dates. If a date is on or after S_i and before S_{i+1} , the corresponding cycle number will be cycle i .

Once the cycles are derived, they can be used to attribute adverse events to a specific cycle based upon the following rules: the start date of the adverse event should be included in a given cycle or if the start date does not fit in any defined cycle, the adverse event will be attributed to the previous cycle if the AE has started within 28 days after the end of the cycle.

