8.1. Treatment Duration

The treatment duration (weeks) is defined as:

$$[(\text{last cycle end date}) - (\text{date of the first study drug administration}) + 1] / 7$$

where 'last cycle end date' is defined in section 4.1.3: Calculation of Cycles, in this document. Summary statistics will be provided for treatment duration for overall treatment (i.e., either pomalidomide or dexamethasone, whichever is earliest for the 'date of the first study drug administration' and whichever is later for the 'last cycle end date'), as well as for pomalidomide and dexamethasone separately.

Additional summaries will be created for all treated subjects, displaying number of subjects treated by the number of cycles administered.

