8.5. Dose Intensity

The delivered dose intensity (DDI) is defined as the cumulative dose delivered divided by the treatment duration and will be calculated for pomalidomide and dexamethasone separately.

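### The last-cycle rule in SAP 4.1.3 has no data cut-off term, so at the first full analysis treatment duration for ongoing subjects can run past the cut-off, and dose intensity is understated when the cut-off falls early in a cycle

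*SAP*

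**What the plan says.** Section 4.1.3 sets the end of the last cycle when the recorded end date is absent or short ("For the last cycle, the end date (if missing or less than 28 days after start of cycle) will be calculated as the start date"). In full, the imputed date is "the start date plus the prescribed cycle length (28) - 1, or the death date, or the discontinuation date, whichever is earlier".

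Section 8.1 carries this date into treatment duration: "where 'last cycle end date' is defined in section 4.1.3: Calculation of Cycles, in this document". Section 8.2 defines cumulative dose from doses taken. Section 8.5 forms the delivered dose intensity (DDI), "defined as the cumulative dose delivered divided by the treatment duration", and section 8.6 divides that by a fixed planned dose intensity (PDI) to give RDI.

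Section 3.1 plans two analyses. The first "will be conducted once all enrolled subjects have completed up to 2 cycles of the IP if having not stopped therapy earlier". The final one comes at study close, "the point when all subjects will have discontinued from the study".

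No other section limits the end date. The last-visit rule in section 6 covers study participation at study close only, and the cut-off of 4 May 2015 in section 12.2 covers the pharmacokinetic population only.

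**The concern.** A subject on treatment at the first full analysis has neither a death date nor a discontinuation date, so only cycle start plus 27 days is left in the rule. If the cut-off falls partway through the cycle, that date lies after the cut-off. The denominator of dose intensity then contains days that have not been observed, while the numerator holds only doses taken.

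POM exposure is a listed secondary endpoint (section 3.3) in a trial whose primary purpose is safety. A fully compliant subject could appear to have had doses reduced or withheld, and a reader could take that for poor tolerability.

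**Working it through.** **Inputs.** End-date rule: section 4.1.3. Duration: 8.1, taken here in days so that it matches the PDI. Cumulative dose: 8.2. DDI and RDI: 8.5 and 8.6. Assumptions not in the SAP: full compliance, POM on days 1–21, dexamethasone (DEX) on days 1, 8, 15 and 22, dosing recorded up to the cut-off, and, for averages, a cut-off equally likely on each of days 1–28.

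**The plan's own figures reproduce.** POM PDI = 4 × 21 / 28 = 3 mg per day. DEX PDI = 160/28 = 5.71 mg per day up to age 75, and 80/28 = 2.86 above.

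**Excess duration.** With the cut-off on day u of the current cycle, the rule ends that cycle on day 28. The excess is 28 − u days: 27 at u = 1, 0 at u = 28, mean 13.5 days (1.9 weeks).

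**POM RDI under the plan's rule.** In current cycle k:

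RDI = 4 × [21(k − 1) + min(u, 21)] / (28k) / 3

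The mean of min(u, 21) over u = 1 to 28 is (231 + 7 × 21)/28 = 13.5, which contributes 4 × 13.5 = 54 mg on average.

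| Current cycle | Worst (u = 1) | u = 14 | u = 21 to 28 | Mean |
|---|---|---|---|---|
| 3 | 172/252 = 68.3% | 224/252 = 88.9% | 100% | (168 + 54)/252 = 88.1% |
| 6 | 424/504 = 84.1% | 476/504 = 94.4% | 100% | (420 + 54)/504 = 94.0% |
| 12 | 928/1008 = 92.1% | 980/1008 = 97.2% | 100% | (924 + 54)/1008 = 97.0% |

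From day 21 all planned POM doses of the cycle have been taken and only rest days remain, so RDI is exact.

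**DEX RDI under the plan's rule.** With n doses taken in the current cycle, RDI = [4(k − 1) + n] / (4k). In cycle 3 this is 9/12, 10/12, 11/12 and 12/12 over the four weeks, mean 87.5%. In cycle 6 the mean is 93.8%. DEX is exact from day 22.

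**Effect of a bare cap at the cut-off.** For cycle 3, day 14, the plan's rule gives 84 days and POM RDI 224/84/3 = 88.9%. The cap gives 70 days and 224/70/3 = 106.7%. Completed cycles only give 168/56/3 = 100%. Averaged over cycle 3, the cap alone gives about 105% for POM and 104% for DEX. It corrects duration but overstates RDI, because dosing days come before rest days within a cycle.

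**Cohort level, illustrative only.** Suppose 10% to 40% of subjects are ongoing, all somewhere in cycles 3 to 12, with a mean POM RDI shortfall of 12 to 3 points. Mean RDI then shifts by 0.10 × 3 = 0.3 to 0.40 × 12 = about 5 points, and mean duration by 0.10 × 13.5 = 1.4 to 0.40 × 13.5 = 5.4 days.

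**The case against.** Crediting a full last cycle has a rationale: the PDI is defined over 28 days, so a full-cycle denominator keeps the rest days in. That stands once the cycle's dosing is complete. Before then, scheduled doses not yet due are treated as undelivered.

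A reader might infer that dose intensity is wrong for every subject caught mid-cycle. It is not: POM is exact on days 21–28, and DEX from day 22 under the assumed schedule. Only duration is affected throughout. Nor are the added days necessarily drug-free; they are days for which no dose has yet been recorded.

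A reader might also compute the effect for a subject partway through cycle 2, where it would be larger. On the natural reading of the trigger in section 3.1, a subject still on treatment has completed two cycles, so cycle 3 is the earliest that applies. Few subjects need be that early: with about 720 enrolled, those who entered first will have more cycles or will have stopped.

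The direction is not always upward. If the current cycle began 28 or more days before the cut-off because the next cycle was delayed, start plus 27 falls before the cut-off.

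The size also depends on data capture, which the SAP does not describe. If dosing records enter the database only when a cycle is complete, the last recorded cycle is already finished and no future days arise.

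Finally, the consequence is limited. Exposure is descriptive, no formal testing is planned (4.1.4), and the gap closes by the final analysis. All of this narrows the point; none of it supplies the missing cut-off.

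**Conclusion.** The point holds in a limited form. For a subject still on treatment at the first full analysis, the stated rule gives a wrong end date rather than leaving a detail open, and sections 8.1, 8.5 and 8.6 pass it on. The excess is less than one cycle per subject and its relative effect shrinks as cycles accumulate. The RDI figures describe one fully compliant ongoing subject whose dosing is recorded to the cut-off; they are not estimates for the trial. The share of subjects ongoing is not stated, so the cohort shift shown is a range under assumed shares. Subjects who have stopped are not affected, because the discontinuation or death date bounds the cycle. The documents do not support any inference that adverse event incidence, the primary endpoint, is distorted. The correction should be made before the first full analysis.

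**What to change.** In section 4.1.3, add the data cut-off date to the dates that can end the last cycle, the earliest to apply, so that treatment duration never passes the cut-off.

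In sections 8.5 and 8.6, state that for subjects still on treatment at the cut-off DDI and RDI are computed over completed cycles only. The alternative is to compare the dose taken with the dose scheduled up to the cut-off. Either returns 100% RDI for a compliant subject. The two changes must go together, since the cap alone would push RDI above 100%.

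The cost is a few words in 4.1.3, a sentence in each of 8.5 and 8.6, and one extra date in the derivation. With the completed-cycles option, the partial current cycle drops out of RDI for ongoing subjects. That is a small loss, because on the natural reading of section 3.1 each of them has at least two completed cycles.

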11.1.6. Electrocardiogram

The overall ECG interpretation will be summarized by presenting the number and percentage of subjects with “Normal” “Abnormal, not clinically significant” and “Abnormal, clinically significant”. Shift from baseline to worst during study, as well as shift from baseline by cycle in the overall ECG interpretation will be displayed in cross-tabulations tabulations.

Other ECG measurements such as QTc will be tabulated with summary statistics (N, Mean, Standard Deviation, Median, Minimum and Maximum) of observed and change from baseline values presented.

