11.1.7. ECOG Performance Status

Shift from baseline to worst during study, shift from baseline to best during study, as well as shift from baseline by cycle in ECOG performance status will be displayed in cross-tabulations.

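### Cycle numbers run from exposure-derived start dates, so a Day 1 assessment made before the cycle's first dose is labelled with the preceding cycle in the by-cycle ECG and ECOG shifts

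*SAP*

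**What the plan says.** Section 4.1.3 builds cycles from dosing data: "The start date of each treatment cycle will be calculated based on study drug exposure records for each subject". For cycle 1 it is specific: "The start date of the first cycle will be the date when the subject receives any study drug". For later cycles it does not say which exposure date is S_i. The rule then covers more than adverse events: "The cycle number for each date of interest, e.g., AE or lab, will be calculated based on the cycle window". A date takes number i when S_i ≤ date < S_{i+1}. There is no allowance for an assessment made shortly before dosing, and the nominal visit is not mentioned.

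Section 3.1 sets the visit schedule: "Safety assessments will be performed during the Screening period and on Day1 (± 1 day) of each cycle". It also states: "Dose modifications and interruptions of the IP are permitted throughout the study".

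Two sections commit to a by-cycle display of scheduled assessments. Section 11.1.6 says "shift from baseline by cycle in the overall ECG interpretation will be displayed", and section 11.1.7 says "shift from baseline by cycle in ECOG performance status will be displayed in cross-tabulations".

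**The concern.** The Day 1 visit has a tolerance on both sides, but the cycle window opens exactly at S_i. A visit on the early side of its permitted window therefore falls outside the cycle it was scheduled for. The same happens when the subject attends on the planned Day 1, dosing is postponed, and S_i moves to the later dosing date.

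For anything measured only at Day 1, such a subject can have two values in cycle i-1 and none in cycle i. The SAP does not say which of two values in one derived cycle enters the table. Section 7.1 prefers retest values, but it says so within the definition of baseline.

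At stake is whether a row labelled with a given cycle in the ECG and ECOG shift tables holds that cycle's Day 1 findings or a mixture of neighbouring cycles. Where postponement is related to the subject's condition, the mixture would also be selective.

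**Working it through.** The SAP gives no figure on this point to reproduce. The check applies its own rule to its own schedule.

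**Inputs**
- 28-day cycles and Day 1 ± 1 day (section 3.1).
- Assignment rule S_i ≤ date < S_{i+1} (section 4.1.3).
- Assumption: S_i is the first-dose date in every cycle. The SAP states this for cycle 1 only.
- Assumption: ECG and ECOG follow the Day 1 schedule that section 3.1 gives for safety assessments.

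**Step 1: visits within the tolerance.** Take S = days 1, 29, 57, 85.

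| Visit relative to S_i | Cycle assigned to Day 1 visits of cycles 1, 2, 3, 4 |
|---|---|
| 1 day before | none, 1, 2, 3 |
| same day | 1, 2, 3, 4 |
| 1 day after | 1, 2, 3, 4 |

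Only early visits are displaced. In cycle 1 an early value precedes all treatment and serves as baseline, so it does no harm. From cycle 2 on, each early visit is labelled one cycle too low.

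**Step 2: postponed dosing.** The Cycle 2 Day 1 visit takes place on day 29, and S_2 = 29 + k for a delay of k days.
- k = 0: S_2 = 29, and the visit goes to cycle 2.
- k = 1, 7 or 14: S_2 = 30, 36 or 43, and the visit goes to cycle 1. A retest on the dosing day goes to cycle 2.

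**Step 3: when displacement has a direction.** The rates here are assumed; none is in the SAP. Let a share q of subjects be delayed, with 10% abnormal among the undelayed and 50% among the delayed.
- By nominal visit, abnormal in cycle 2 = q × 50% + (1 − q) × 10%.
- Under the rule without a retest, only undelayed subjects contribute, so 10%.
- Under the rule with every retest normal, (1 − q) × 10%.

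| q | Nominal visit | Rule, no retest | Rule, all retests normal |
|---|---|---|---|
| 10% | 14% | 10% | 9% |
| 20% | 18% | 10% | 8% |
| 30% | 22% | 10% | 7% |

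If delay is unrelated to abnormality (10% in both groups) and there is no retest, the nominal figure is q × 10% + (1 − q) × 10% = 10%, the same as under the rule. Cycle 2 then loses subjects but is not biased.

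**Step 4: which outputs use the cycle number.** Laboratory shifts (section 11.1.4) and vital-sign shifts (section 11.1.5) go to the worst value during treatment. The worst shifts for ECG and the worst and best shifts for ECOG also ignore cycle. Adverse events are placed by onset date, for which a date window is suitable, and overall incidence does not depend on cycle. That leaves the by-cycle ECG and ECOG shifts.

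**The case against.** The strongest reply is that a value taken before any cycle i drug reflects exposure up to cycle i-1, so numbering it i-1 is a legitimate convention. This fails on consistency. The rule works on dates, so an equally pre-dose value taken on the dosing day is numbered i. Two clinically equivalent assessments a day apart get different cycle numbers.

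Other parts of the reply stand:
- The first-dose reading of S_i is inferred beyond cycle 1. If exposure records carry a recorded cycle start, a delay need not move S_i. If later cycles start with whichever drug is given, as cycle 1 does, holding one of the two drugs would not move it either.
- Appendix B lists ECOG shifts to worst and best only, and no by-cycle shift table. The commitments in the text of sections 11.1.6 and 11.1.7 remain.
- No formal hypothesis testing is planned, and the outputs concerned are descriptive.

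Two stronger readings are tempting. A reader might infer that one Day 1 value in three is misplaced, because one of the three permitted days is early. The SAP gives a tolerance, not a distribution of visits, and if visit and dosing move together nothing is displaced. A reader might also infer that later cycles are bound to look better than they were. An early visit has no inherent link to fitness, the SAP gives no reasons for or rates of delay, and a displaced value is not lost: it moves to the preceding cycle, which may then look worse.

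**Conclusion.** The point holds as a minor defect of specification. On the first-dose reading of S_i, section 4.1.3 labels some Day 1 assessments with the preceding cycle, and the visit tolerance in section 3.1 makes this possible without any departure from schedule. The consequence is misclassification in the by-cycle ECG and ECOG shifts, with no rule for the case where two values share a cycle.

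The share of values affected cannot be stated from the SAP. The direction is favourable to later cycles only through postponed dosing, and only if postponement goes with worse findings. The percentages in the working show the mechanism under assumed rates and are not an estimate. The primary endpoint is untouched. Section 12.3.2 also summarises POM concentrations by cycle, but the SAP does not say whether section 4.1.3 governs them, so they are not counted here.

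**What to change.** Amend section 4.1.3 in three respects:
- Scheduled assessments that are summarised by cycle, at least ECG and ECOG, take the cycle number of their nominal visit, including visits at which dosing was postponed.
- Adverse events and unscheduled assessments keep the date-window rule. State which exposure date defines S_i after cycle 1.
- State which value enters a by-cycle table when several carry the same cycle number. If the retest preference of section 7.1 is meant to extend to these tables, say so, because a retest at restart would then replace the value seen at the postponed visit.

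Opening the window one day before S_i is not an adequate substitute, because it would not recover a visit followed by a delay of more than one day.

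The cost is two or three sentences and a small change in the derivation, with no new data, provided the nominal visit label is held in the database. The SAP does not confirm this, so it should be checked first.
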